2.3 POTENTIAL RISKS AND BENEFITS

2.3.1 KNOWN POTENTIAL RISKS

Known **potential risks of** the BGI and the associated implant procedure may include:

- Adverse Result to Patient
- Aborted Procedure
- Bleeding
- Cataract formation or progression
- Choroidal detachment
- Choroidal effusion requiring surgical drainage
- Channel blockage
- Chronic iritis
- Corneal Haze/Opacity
- Corneal false tract above Descemet's membrane
- Corneal Neovascularization
- · Conjunctival overgrowth
- Corneal endothelial touch
- Death
- Delayed Procedure
- Deposits on device
- Device malfunction
- Device Migration or Dislodgement
- Device Rejection
- Endophthalmitis
- Flat anterior chamber requiring anterior chamber reformation
- Focal conjunctival hyperplasia
- Infection

- Inflammation including iris, macular and corneal edema
- Hematoma or Hemorrhage including suprachoroidal or vitreous hemorrhage
- Hyphema
- Hypotony (IOP < 6 mmHg when conscious)
- Hypotony maculopathy
- Increased tearing
- Ocular Trauma
- Peripheral flow/ wound leak
- Permanent Loss of Vision
- Phthisis / atrophy (shrinkage of the eye)
- Ptosis
- Pyrogenic
- Re-intervention
- Retinal Detachment
- Secondary surgical interventions
- Substantial increase in IOP vs. baseline
- Severe Irritation including Chronic Iritis
- Temporary Hypotony associated with General Anesthesia
- Temporary Loss of Vision
- Toxicity
- User Dissatisfaction
- Retrograde flow and increased IOP with swimming/diving

There may also be other risks related to the BGI and associated implant procedure that are not listed or that are not known at this time. This study will help characterize the adverse events associated with the BGI implant.

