8.1.6 PRE-SPECIFIED LIST OF ADVERSE EVENTS

Adverse events listed below are provided on the case report form along with a method for recording other adverse events not listed, based on the recognized standard ANSI Z80.27-2014.⁷

- Corneal edema
- Progression of cataract requiring cataract extraction

- Wound leak
- Suture abscess or other local infection
- Endophthalmitis
- Chronic iritis
- Hyphema
- Strabismus
- Macular edema
- Vitreous hemorrhage
- Suprachoroidal hemorrhage
- Retinal detachment
- Device malfunction
- Device blockage not requiring surgical revision
- Device blockage requiring surgical revision
- Implant migration (of any kind) not requiring surgical intervention
- Implant migration requiring surgical revision
- Implant exposure or extrusion
- Flat anterior chamber requiring anterior chamber reformation
- Hypotony (e.g., IOP <6 mmHG and associated with concomitant hypotonous findings are noted, including: Corneal edema/folds, shallow anterior chamber, hypotonous maculopathy, significant choroidal detachments or effusion)
- Hypotony maculopathy
- Choroidal effusion requiring surgical drainage
- Substantial increase in IOP vs. baseline (defined as >10 mmHg)
- Substantial visual field loss vs. baseline (e.g., 10 db loss)
- Substantial visual acuity loss vs. baseline (e.g. 10 or more ETDRS letters)
- Event requiring unplanned ocular surgical re-intervention

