The Sponsor and linvestigator will distinguish between the serious adverse events related to the investigational device and those related to the procedures (any procedure specific to the clinical investigation). An adverse event can be related both to procedures and the investigational device. Complications of procedures are considered not related if the said procedures would have been applied to the patients also in the absence of investigational device use/application.

Related to Device - Events reasonably anticipated to be related to the physical presence of the device, e.g. erosion, a device deficiency, dislodgment.

Related to Procedure — Events reasonably anticipated to be related to procedures (pertaining to implant) described in this protocol.

NOTE: Procedure related events refers to the procedure related to the initial application of the investigational medical device only and therefore not to any other procedures or treatments applied later throughout the clinical investigation, for instance to treat (serious) adverse events.

In some particular cases the event may be not adequately assessed because information is insufficient or contradictory and/or the data cannot be verified or supplemented. The Ssponsor and the Investigators will make the maximum effort to define and categorize the event and avoid these situations. Where the Sponsor remains uncertain about classifying the serious event, it should not exclude the relatedness and classify the event as "possible".

Particular attention shall be given to the causality evaluation of unanticipated serious adverse (device) events. The occurrence of unanticipated events related to the use of the device (USADE) could suggest that the clinical investigation places subjects at increased risk of harm than was to be expected beforehand.

All AEs will be collected from the time of informed consent through the end of the study. Death should not be recorded as a separate adverse event, but rather as an outcome of the specific SAE which led to the subject's death. Adverse Events that would be reasonably expected to be associated with any surgical procedure (e.g.: anesthesia associated nausea, surgical site pain) will not be categorized as procedure or device related in the 30 days post the surgical procedure.

Notes:

- 1. Any current condition that is recorded as a pre-existing condition is not an AE, unless there is a worsening of that condition in terms of nature, severity, or degree of incidence.

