- 2. Technical observations an undesirable device event that does not result in a medically undesirable situation for the subject is not an AE.
- 3. Planned hospitalization for a procedure required by this protocol is not an AE. However, complications during the course of that planned hospitalization that prolong the anticipated duration of the hospitalization do constitute SAEs.
- 4. Elective hospitalization for a pre-existing illness does not constitute an SAE unless the illness has worsened in the nature, severity or degree of the condition with respect to baseline.
- Device dislodgment/expulsion will not be collected as an AE, but rather as a device
 deficiency. If device migration results in a clinical symptom, report this as an AE in addition
 to the device deficiency report documenting device dislodgment/expulsion.
- 6. Lack of efficacy or diminished therapeutic response does not constitute an AE since failure to receive therapeutic benefit is an issue of efficacy, not safety. This includes symptoms that recur in the context of device deficiency leading to loss of therapy.

Removal and/or replacement of the device due to malfunction would be considered a device related adverse event

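### The protocol does not reconcile Note 6 of section 8.2.1 and section 8.5 with the AE list in section 8.1.6, so a pressure rise, blockage or malfunction after loss of device function can be filed either way

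*Protocol*

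**What the plan says.** **Passages that leave the event out of the AE data**

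- Protocol 8.2.1, Note 6, reads: "Lack of efficacy or diminished therapeutic response does not constitute an AE". The reason it gives is that missing benefit belongs to efficacy and not to safety. It then adds: "This includes symptoms that recur in the context of device deficiency leading to loss of therapy".
- Protocol 8.2.1, Note 2: an undesirable device event with no medically undesirable result for the subject is a technical observation and not an AE.
- Protocol 8.5: the example is a device that has lost patency without causing discomfort. It may stay in place while a second device or another treatment is used. From this the section concludes that a deficiency need not produce an AE or SAE.

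**Passages that count it**

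- Protocol 2.3.1 names "Substantial increase in IOP vs. baseline" as a known potential risk.
- Protocol 8.1.6 puts it on the pre-specified AE list with a threshold: "Substantial increase in IOP vs. baseline (defined as >10 mmHg". The same list has device malfunction, "Device blockage not requiring surgical revision", and blockage that does require revision. The list is printed on the case report form.
- Protocol 8.2.1, Note 1: a pre-existing condition is not an AE "unless there is a worsening of that condition in terms of nature, severity, or degree of incidence".
- Protocol 8.2.1, directly after Note 6: "Removal and/or replacement of the device due to malfunction would be considered a device related adverse event".
- Protocol 8.5: an AE that accompanies a device deficiency goes on the AE form.

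No sentence says which group prevails. SAP 4.1 summarises reported AEs, ADEs, SAEs and UADEs in the implanted eye through 6 months and adds no rule on this point.

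**The concern.** The device's only therapeutic action is to lower pressure. When it stops draining, one clinical course can be described as lost efficacy, as a device deficiency, or as an AE. Note 6 sets no limit at the pre-implant level and expressly takes in symptoms, so a site could apply it to a pressure rise that section 8.1.6 lists. A site following section 8.5 could record a blocked device as a deficiency only, although section 8.1.6 lists blockage as an AE even without surgical revision.

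The stake is the safety endpoint, which is the set of AE-class rates through 6 months (protocol 4.1.1). An event not filed as an AE is absent from the SAP 4.1 table and is not graded as an AE for seriousness or relatedness. It therefore cannot enter the halting count in section 8.7. Such an omission would favour the device, and section 10.6.1 provides no masking at the three sites.

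**Working it through.** The documents give no computed figure on this point, and the sample size of 10 is not statistically derived (protocol 10.5). There is nothing to reproduce. The check is a comparison of passages, followed by a statement of scale.

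**Step 1. Where the IOP rules can collide.** The list item is met when follow-up IOP exceeds baseline + 10 mmHg. Eligible baseline IOP is 21 to 50 mmHg (protocol 5.1).

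| Baseline (mmHg) | Listed AE if IOP is above (mmHg) |
|---|---|
| 21 | 21 + 10 = 31 |
| 30 (illustrative) | 30 + 10 = 40 |
| 50 | 50 + 10 = 60 |

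An illustrative eye that goes from 30 to 42 mmHg has risen by 42 − 30 = 12 mmHg, which exceeds 10, so it meets the list item. An eye that returns to 30 does not. Note 6 and the IOP item can therefore collide only above baseline + 10.

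**Step 2. Passages side by side, for each event after loss of device function.**

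| Event | Counts it | Leaves it out | Compatible as written? |
|---|---|---|---|
| IOP or symptoms back to the pre-implant level | none specific | Note 6 | Yes: efficacy |
| IOP more than 10 mmHg above baseline | 8.1.6, Note 1 | Note 6, read broadly | Yes, if Note 6 stops at baseline, which is not stated |
| Symptom worse than baseline | Note 1 | Note 6, read broadly | Same condition |
| Blockage, device left in place | 8.1.6 | 8.5 example; Note 2 if no clinical effect | No |
| Malfunction, device left in place | 8.1.6 | 8.5; Note 2 if no clinical effect | No |
| Malfunction, device removed or replaced | 8.1.6; sentence after Note 6 | none | Yes |

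The blockage row assumes that lost patency in section 8.5 and blockage in section 8.1.6 are the same event.

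**Step 3. Scale in the AE table.** Take N = 10. One subject moves a participant-level rate by 1/10 = 10 percentage points. The exact (Clopper-Pearson) 95% limits for x of n are the 0.025 quantile of Beta(x, n − x + 1) and the 0.975 quantile of Beta(x + 1, n − x). At x = 0 the lower limit is 0.

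| x/10 | Rate | 95% interval |
|---|---|---|
| 0/10 | 0% | 0 to 30.8% |
| 1/10 | 10% | 0.3 to 44.5% |
| 2/10 | 20% | 2.5 to 55.6% |
| 3/10 | 30% | 6.7 to 65.2% |

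**Step 4. Scale in the halting rule.** Section 8.7 halts the study when 2 of the first 5 subjects, or 3 in total, have a serious device- or procedure-related AE. One unfiled case changes the outcome only if it is serious, related, not entered through another listed event, and the count stands one short of the limit.

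**The case against.** The strongest reply is that the protocol, read as a whole, already sorts these events. Note 6 speaks of failing to receive benefit and of symptoms that recur, and recurrence naturally means a return to the earlier state. A pressure more than 10 mmHg above the pre-implant value is a new worsening. Note 1, in the same list of notes, makes worsening an AE, and the IOP item with its threshold is on the form the site completes. AEs are actively sought at every visit (section 8.3), and removal or replacement for malfunction is a device-related AE.

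This stands for the IOP item. A reader might infer that Note 6 keeps every consequence of lost device function out of the AE data. The text does not support that: Note 6 mentions no rise above baseline, and several passages favour counting one.

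A reader might also infer that such events would disappear from the trial's data. That is not supported either. IOP is summarised for effectiveness, deficiencies have their own form, key effectiveness variables are listed by subject (protocol 10.4.9), and SAP section 3 treats explanted subjects as failures. The DSMB and the two-monthly safety review can act even if the stopping rule is not met.

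The reply is weaker in three places:

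- Nothing says that Note 1 or the list overrides Note 6.
- Sending an AE that accompanies a deficiency to the AE form does not help when the question is whether there is an AE.
- The removal or replacement sentence, and the SAP's explant rule, may not reach an eye whose blocked device is left in place, which section 8.5 allows.

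**Conclusion.** The point holds as an unresolved ambiguity for the IOP item and a more direct conflict for blockage and malfunction. A consistent reading of the IOP item exists, but each site has to infer it. For blockage and malfunction with the device left in place, sections 8.1.6 and 8.5 give different answers. AE and ADE rates, and possibly the halting count, could depend on which passage a site follows.

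The size is 10 percentage points per reclassified subject, assuming N = 10. The number of affected subjects is not given and may be zero. A reader might infer that sites have in fact filed like events differently; the documents offer no evidence of that. The effect on the halting rule rests on the chain of conditions in step 4 of the working and is a possibility only.

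One further assumption: the SAP cites the protocol as number 6054, formerly 4039. The text reviewed here is 4039 version 9.0, so the conclusion applies to any later version only if the wording is unchanged.

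**What to change.** **Wording.** Reconcile section 8.2.1 Note 6, section 8.5 and section 8.1.6 with one statement in the protocol or AE guideline:

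- Note 6 covers only a return to, and not beyond, the pre-implant level of IOP or symptoms.
- Any event on the 8.1.6 list is reported as an AE whether or not loss of device function caused it.

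The section 8.5 example and Note 2 should be edited to agree. A rise between baseline and baseline + 10 mmHg would then be judged under Note 1.

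**Data already collected.** Programmatically flag implanted-eye IOP more than 10 mmHg above baseline, and blockage or malfunction entries, that have no matching AE. Send each to the investigator as a query. Show unresolved cases in a supportive listing beside the SAP 4.1 table. They should not be put straight into that table, because section 8.2.1 requires causality to be assessed by clinical judgement and a derived reading has had no such assessment.

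**Cost.** The cost is a short text change, one programmed check and a few queries. Tonometry is scheduled at baseline and at every follow-up visit (protocol 7.2.5), so no new measurements are needed. The downside is a possibly higher AE count.

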8.3 TIME PERIOD AND FREQUENCY FOR EVENT ASSESSMENT AND FOLLOW-UP

Adverse events will be monitored through study closure. Each scheduled and unscheduled follow-up visit will include active ascertainment of new adverse events, as well as follow-up of previously reported, ongoing adverse events. All study subjects will be educated on the anticipated adverse events associated with the BGI and ocular surgery through the consenting process. They will be instructed to contact their physician if they experience any adverse events during their participation in the trial. All adverse events will be documented on the adverse event forms.

8.4 REPORTING PROCEDURES

8.4.1 ADVERSE EVENT REPORTING

The Investigator will monitor the occurrence of adverse events for each enrolled Subject. Adverse events reported by the Subject to the Investigator, confirmed by the Investigator, and documented in medical records must be reported on the adverse event form based on the requirements of the study CIP. All ADEs, SAEs, SADEs, and USADEs will be reported to all Investigators and IRBs and/or Ethics Committees participating in the study per their reporting requirements. This is done by means of an interim report or a final study report prepared by the Sponsor.

8.4.2 SERIOUS ADVERSE EVENT REPORTING

Serious adverse events are to be reported to the Sponsor by the Investigator within three working days of becoming aware of the event in compliance with MEDDEV 2.7/3 revision 3 May 2015; Guidelines on Medical Devices Clinical Investigations: Serious Adverse Event Reporting Under Directives 90/385/Eec And 93/42/EEC.

8.5 DEVICE DEFICIENCIES

Device deficiencies are defined as inadequacy of an investigational medical device related to its identity, quality, durability, reliability, safety or performance. This may include malfunctions, use error, or inadequacy in the information supplied by the manufacturer.

All suspected investigational device deficiencies should be documented on the appropriate CRF. The Sponsor will investigate all suspected device deficiencies.

Note: a device deficiency can include a device malfunction (i.e.: failure to perform to specifications), and may also include other deficiencies (e.g.: ambiguity of labelling).

For the BGI, not all device deficiencies will lead to an explant. For example, if patency is lost but the device is not causing discomfort, the Investigator and study subject may elect to leave the device in place while implanting a second device or seeking alternative treatment. Thus a device deficiency may not necessarily lead to an AE or SAE. If explanted, a device with a suspected malfunction should be returned to MicroOptx for analysis. If it is not possible to return the device, the reason it could not be returned as well as its final disposition should be documented. Note that reporting of device deficiencies shall be separate from adverse event reporting. If there should be an adverse event associated with the device deficiency, then that adverse event should be reported on an adverse event CRF.

8.6 SUBJECT DEATH

A subject death during the study should be reported to the Sponsor as soon as possible and, in any event, within two working days of notification to the Investigator. The center's IRB or Ethics Committee must be notified of any deaths in accordance with that center's IRB or Ethics Committee policies and procedures. Notification of death should include a detailed narrative (death letter) that provides detailed information describing the circumstances surrounding the death and is signed by the principal Investigator or authorized Sub-Investigator. The death letter should include all of the following:

- · Date and time of death
- Place death occurred
- Immediate cause of death
- Whether or not the death was witnessed
- Device status at the time of death, if known
- Any other circumstances surrounding the death
- Approximate time interval from the initiating event to death (temporal course)
- Investigator or sub-Investigator signature and date

Any information listed above that is unavailable or unknown must be specified as such in the death letter. If the subject expired in the hospital, the following documentation should also be submitted:

- A copy of the medical records for that admission (e.g., consults, test results, operative reports, and/or progress notes from the hospital chart)
- Death certificate (if available)
- Autopsy report (if applicable)

If the subject expired outside of the hospital (e.g., home):

- A copy of the most recent clinic visit (if not already submitted to the Sponsor)
- Death certificate (if available)

As applicable per local country regulation, the event should be reported by the Investigator to the appropriate regulatory bodies.

8.7 STUDY HALTING RULES

There are no statistically-based rules related to early trial termination. However, if two of the first five subjects experience a serious device or procedure related adverse event, or if three total subjects experience a serious device or procedure related adverse event, the study will be halted until the time an acceptable (to FDA and sponsor) mitigation can be implemented. If no such mitigation is possible, the study will be terminated. In addition, the Sponsor and independent Medical Director will review safety data every two months, including the emergence of serious adverse events and unanticipated adverse device effects, and will convene a special session of the DSMB if the observed risks appear greater than expected, even if the stopping rule is not met.

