Number of Sites	Three sites in the United States of America.				
enrolling participants:					
Study Size:	10 subjects.				
Primary Effectiveness	Overall responder rate, with responder defined as achieving at least 20%				
Endpoint:	reduction from baseline in IOP.				
	Mean change from baseline in IOP				
Secondary Effectiveness	Responder rate, with responder defined as achieving follow-up				
Endpoints:	IOP less than or equal to 14 mmHg				
	Change in IOP-lowering medications				
	Changes from baseline in the Schirmer Tear Test				
Exploratory Endpoints:	Treatment satisfaction questionnaire at six months post implant				
	(TSQ)				
	Rate of all AEs, ADEs, SAEs, SADEs and UADEs through the six months post-				
Safety Endpoint:	implant visit, with continuing follow up of ADEs, SAEs, SADEs and UADEs				
	throughout the study.				
	Screening visit which includes Informed Consent, eligibility, and				
	baseline data collection				
	Implant visit with surgical implantation of BGI within 42 days of				
	screening; may be same day as baseline data collection				
	One day post-implant				
	One week visit: 5-9 days post-implant				
	Two week visit: 11-17 days post-implant				
	1 month visit: 25-35 days post-implant				
	2 month visit: 50-70 days post-implant				
Ctudu Cabadular	3 month visit: 75-105 days post-implant				
Study Schedule:	4.5 month visit: 125-150 days post-implant				
	6 month visit: 168-196 days post-implant – Primary End Point				
	evaluation				
	8 month visit: 225-255 days post-implant				
	10 month visit: 285-315 days post implant				
	12 month visit: 330-390 days post-implant				
	15 month visit: 440-470 days post implant				
	18 month visit: 530-560 days post implant				
	21 month visit: 620-650 days post implant				
	24 month visit: 690 – 750 days post-implant				
	Primary endpoints will be evaluated at six months, and all subjects will be				
Study Duration:	followed through 24 months post-implant. Expected subject accrual is one				
	to three months.				
Participant Duration:	24 months, though study subjects may be enrolled in a long-term follow-				
	up registry after the 24 month visit.				

SCHEMATIC OF STUDY DESIGN

Long Term Follow-up Evaluation

- •Month 8 (225-255 days post-implant)
- •Month 10 (285-315 days)
- •Month 12 (330-390 days)
- •Month 15 (440-470 days)
- •Month 18 (530-560 days)
- •Month 21 (620-650 days)
- •Month 24 (690-750 days)

KEY ROLES

Sponsor:

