8.8 SAFETY OVERSIGHT

A Data Safety Monitoring Board (DSMB) will be assembled to routinely monitor ongoing safety of trial participants. The DSMB will meet at least quarterly and, upon data review, make recommendations to the sponsor to:

- Continue the trial as planned
- Continue the trial with modification(s), or
- Terminate the trial due to safety concerns.

A DSMB charter will be developed separately in a cooperative effort between sponsor and the DSMB.

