10.5 SAMPLE SIZE

This trial is a first-in-human feasibility trial of the Brown Glaucoma Implant. No formal tests of hypothesis are planned, and so sample size is not statistically derived. A total of ten enrolled and implanted subjects are believed to be sufficient to confirm preclinical findings, provide evidence of feasibility of efficacy, and determine whether or not the observed safety profile justifies further study.

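### Section 8.7 sets a stricter halting tier for the first five subjects but no pause before the sixth implant, so events that arise over months would meet the tier only after most or all ten eyes are implanted

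*Protocol*

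**What the plan says.** Protocol 8.7 opens by disclaiming a statistical basis: "There are no statistically-based rules related to early trial termination". It then gives the only numeric rule. The trigger is "if two of the first five subjects experience a serious device or procedure related adverse event, or if three total subjects experience" such an event, and the action is that "the study will be halted until the time an acceptable (to FDA and sponsor) mitigation can be implemented". If no mitigation is possible, the study is terminated.

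The sections that determine how this works in practice are:

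- **Size and speed.** Protocol 10.5: "A total of ten enrolled and implanted subjects are believed to be sufficient". The Protocol Summary adds, under Study Duration, "Expected subject accrual is one" to three months, and names three sites. Section 7.2.2 asks for implantation promptly after baseline, with no wait between subjects.
- **Information flow.** Protocol 8.4.2: "Serious adverse events are to be reported to the Sponsor by the Investigator within three working days of becoming aware of the event". For investigators and IRBs, 8.4.1 covers device effects and serious events and says "This is done by means of an interim report or a final study report prepared by the Sponsor".
- **Review.** Under 8.7 the Sponsor and Medical Director review safety every two months. Under 8.8, "The DSMB will meet at least quarterly".
- **After a halt.** Section 5.7 promises a Sponsor plan for suspension or termination. Section 4.1 follows all subjects for two years. Section 8.5 allows a second device if the first loses patency. Section 8.7 does not say which of these activities a halt stops.

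**The concern.** With ten subjects, a separate and stricter tier for the first five is useful mainly if its result is known before subjects 6 to 10 are implanted. The protocol does not state that purpose, but it is the natural reading of the tier. Nothing links the sixth implant to the outcome of the first five. If accrual is fast and harm is slow, the tier is met when there are few or no first implants left to prevent.

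This is a first-in-human device. Section 2.3.4 names infection and hypotony as perhaps its most serious risks, and section 2.1.2.3, writing of minimally invasive glaucoma surgery, says infection may appear years afterwards. Slow events are therefore a realistic case. Two smaller gaps add to this: a halt has no stated scope, and the only stated route by which other implanting surgeons learn of a serious related event is a periodic or final report.

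**Working it through.** The documents give no operating characteristics for the rule, so there is no stated figure to reproduce.

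**Inputs from the documents.** Ten implants (10.5); accrual A of 30, 60 or 90 days (Protocol Summary), taken as the span of the implants; triggers of at least 2 of the first 5 or at least 3 in total (8.7); reporting within three working days (8.4.2), taken as 5 calendar days.

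**Assumptions.** Even spacing. A 40% chance of a serious related event by day 183. Three timing patterns, with F(x) the probability of an event within x days of implant:

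- constant hazard: F(x) = 1 − 0.6^(x/183)
- front-loaded (Weibull, shape 0.5): F(x) = 1 − 0.6^√(x/183)
- all within 14 days: F(x) = 0.4 × min(x/14, 1)

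**Step 1: calendar.** Implant i falls on day A(i − 1)/9. Implant 6 is on day 17, 33 or 50, and implant 10 on day 30, 60 or 90.

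**Step 2: rule met before implant 6.** At that time only subjects 1 to 5 count, so the two-of-five tier decides. Subject i has x_i = A(6 − i)/9 − 5 days in which an event can occur and be reported (zero if negative). With q_i = F(x_i),

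P = 1 − Π(1 − q_i) − Σ q_i Π_{j≠i}(1 − q_j).

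Example, A = 60, constant hazard: x = 28.3, 21.7, 15.0, 8.3, 1.7; q = 0.076, 0.059, 0.041, 0.023, 0.005; P = 1 − 0.811 − 0.175 = 0.014.

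| Timing (40% rate) | 1 month | 2 months | 3 months |
|---|---|---|---|
| Constant hazard | 0.2% | 1.4% | 3.7% |
| Front-loaded | 4% | 12% | 19% |
| All within 14 days | 16% | 47% | 57% |

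For comparison, two of the first five have an event by six months with probability 1 − 0.6^5 − 5(0.4)(0.6^4) = 1 − 0.078 − 0.259 = 66%.

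**Step 3: other rates.** With 0.6 replaced by 0.8 (20% rate), the constant-hazard row is at most 0.8% and the front-loaded row at most 5%. With 0.4 (60% rate), the front-loaded row reaches 41% at three months.

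**Step 4: either tier met before implant 10, by simulation at the 40% rate.** About 2%, 10% and 20% at constant hazard, and 17%, 32% and 44% front-loaded (three months taken as 91 days).

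**Step 5: a second model as a check.** Rate 30%, lag 4 days, event times uniform. The table gives the mean number of eyes implanted when the two-of-five tier is met, and in brackets the share of those trials with all ten implanted.

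| Event window | 1 month | 2 months | 3 months |
|---|---|---|---|
| 7 days | 5.4 (0%) | 4.2 (0%) | 3.8 (0%) |
| 30 days | 8.6 (47%) | 6.1 (1%) | 5.1 (0%) |
| 6 months | 10.0 (98%) | 9.8 (91%) | 9.4 (80%) |

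**Step 6: effect of a pause.** As an illustration, let implant 6 wait until subject 5 reaches day 35, the end of the Month 1 window. It moves from day 5A/9 to day 4A/9 + 35, a delay of 35 − A/9 = 32, 28 or 25 days. The probabilities in step 2 rise to 8%, 10% and 13% (constant hazard), 27%, 30% and 33% (front-loaded), and 66% throughout (within 14 days).

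**The case against.** Two stronger readings are tempting, and the documents support neither.

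First, a reader might infer that the rule cannot be met until accrual is over, because reviews are two-monthly and DSMB meetings quarterly. The trigger in 8.7 is not tied to those meetings; the two-monthly review is introduced as an addition. Serious events reach the Sponsor within working days, and the rule can be met from the second subject on. With all events in the first week, about four to five eyes are implanted when the two-of-five tier is met, and never all ten (step 5).

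Second, a reader might infer that halting the study leaves implants untouched, or suspends follow-up of eyes already implanted. A study halt ordinarily includes new implants. Section 5.7 requires a plan, 4.1 sets two years of follow-up, and 8.3 monitors adverse events through study closure. The fault is an undefined scope.

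There are also informal controls. The Sponsor receives every serious event, hand-delivers the devices (6.1.1, 6.2) and proctors the first three implants at each centre (2.3.3), up to nine of ten. It could withhold the next implant at once. Section 10.4.6.1 describes ongoing safety assessment, 8.7 allows a special DSMB session before the rule is met, and the IRB may suspend the trial (12.1). These are real protections, but none obliges anyone to wait after subject 5.

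Three uncertainties remain. The DSMB charter is a separate document and may contain a hold. If accrual counts consent, which is how 10.6.1 defines enrolment, the last implant could come as late as day 72 to 132 (30 + 42 to 90 + 42), which weakens the timing. The baseline-to-implant limit is 30 days in 7.2.2 and the screening-to-implant limit 42 days in the Protocol Summary, and these must be reconciled. Lastly, SAP 4.2 says available implant videos have already been reviewed. If all ten implants are done, a pause is moot for this cohort, while halt scope and notification still matter for follow-up and second devices.

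**Conclusion.** The concern holds in limited form. No section of the public protocol pauses implants after subject 5, and the expected accrual is short against the six-month safety period. For serious related events arising over months, the two-of-five tier gives subjects 6 to 10 little protection: it is met before implant 6 in at most about 4% of trials at constant hazard and 19% when front-loaded, against 66% in which two of the first five have an event by six months. For events within two weeks it works partly, at 16% to 57%.

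These figures rest on an assumed 40% rate, assumed timing, even spacing, a five-day lag and accrual measured in implants. The direction of the result for slow events is the same at every rate tried, but the size is not. Halt scope and cross-site notice are points of clarification.

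**What to change.** 1. **Section 8.7, pause.** State that subject 6 is not implanted until the first five have completed an already scheduled visit chosen by the DSMB, and the DSMB has reviewed their safety data. The visit is for the DSMB to set; Month 1 in step 6 is only an illustration. Even that pause would leave many slow events undetected, so the DSMB should weigh a later visit against the longer wait.
2. **Section 8.7, scope.** State that a halt covers new implants at all sites while scheduled safety follow-up of implanted subjects continues, and reconcile this with 5.7 and the 24-month follow-up. How a halt bears on second devices under 8.5 is for the sponsor and DSMB to decide.
3. **Section 8.4.1, notice.** Require the Sponsor to notify all implanting investigators and the DSMB promptly of each serious related event, in place of relying on the interim or final report.

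If the DSMB charter already contains a hold, cite it in 8.7 so that it binds the sites.

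The cost is protocol wording, one DSMB review, and 25 to 32 days of added accrual in the illustration plus the time the review takes, against 24 months of follow-up. A later visit costs more. No subjects or procedures are added.
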